2.3 Nitrite Therapy: Novel Approaches for Treatment for Ischemic Diseases

Until recently, nitrite was thought to have minimal biological activity *in vivo*. However, it is now known that nitrite undergoes reductive conversion to NO by a number of mechanisms including the enzymatic actions of xanthine oxidoreductase, non-enzymatic disproportionation, and a hemoglobin reductase activity that is under allosteric control. These mechanisms of nitrite reduction favor bioconversion of nitrite to NO under the hypoxic and acidic conditions present during ischemia and have led to a series of experimental studies demonstrating that therapeutic administration of low dose nitrite in animal models of ischemia and reperfusion result in dramatic cytoprotection in the liver, heart, lungs, brain and kidney.

The mechanism of nitrite cytoprotection in ischemic diseases is not fully known but does depend on the release of NO. For example, there is a loss of cytoprotection when animals were treated with the NO scavenger carboxy-PTIO, suggesting the importance of NO in the mechanism of cytoprotection. Pretreatment of animals with an NO synthase inhibitor or use of eNOS knockout mice⁴² did not inhibit cytoprotection, proving that the nitrite effect is NO synthase-independent. Reactive oxygen species (ROS) generation by the mitochondria has been determined to be a necessary component of mitochondrial signaling in cytoprotection. However, the large burst of oxidizing reactive oxygen species generated after reperfusion following ischemia can also contribute to cellular injury, necrosis and apoptosis. S-nitrosation of complex I of the electron transport chain by S-nitroso glutathione inhibits the activity of this complex and will decrease mitochondria-derived reactive oxygen species formation during reperfusion, an effect associated with cellular cytoprotection. Nitrite can similarly nitrosate complex I during ischemia and reperfusion. This modification limits complex I dependent reperfusion ROS formation, activation of the mitochondrial permeability transition pore, and cytochrome C release.

Recent studies indicate that circulating nitrite is the transducer of protective effects of inhaled nitric oxide in human liver transplantation in which therapy improved the rate of recovery of liver function post-transplantation and decreased hospital length of stays. Inhaled NO (iNO) was approved by the U.S. Food and Drug Administration in December, 1999, for the treatment of persistent pulmonary hypertension of the newborn. Over the last decade, the primary advantage of iNO was seen to be its ability to selectively decrease pulmonary vascular resistance with minimal effects on systemic blood pressure; however, there is currently much interest in exploring its other benefits, including its antioxidant properties and cytoprotective capabilities

(22). In animal studies, iNO decreased infarct size and left ventricular dysfunction after ischemia-reperfusion injury, increased coronary artery patency after thrombosis, increased blood flow in brain, kidney and peripheral vasculature, decreased leukocyte adhesion in bowel during ischemia reperfusion, and decreased platelet aggregation (23). Date *et al* reported the use of iNO in 15 out of 32 patients who suffered from immediate severe allograft dysfunction with iNO at 20-60 ppm following lung transplantation. The mortality was significantly lower in the iNO group (7% and 24%, respectively). The gross benefits reported were that iNO improves oxygenation, decreases pulmonary artery pressure, shortens the period of postoperative mechanical ventilation, and reduces airway complications and mortality (24). Likewise, a recent retrospective study also reported an improvement of overall respiratory functions. The authors encouraged the administration of iNO for the prevention and treatment of early graft failure in lung transplant recipients (25). Varadarajan *et al* were the first group to study the relationship between NO metabolism and IRI in human liver transplantation (26). From their study, they concluded that reduced eNOS expression contributed to IRI one hour after portal reperfusion. On the other hand, iNOS did not contribute to early IRI after human liver transplantation. Clinical and mechanistic reports on therapeutic use of iNO have demonstrated improved NO bioavailability in extrapulmonary tissues specifically in the setting of ischemic stress although how these effects are mediated remains unclear. Specifically, iNO improved human forearm blood flow in tourniquet induced ischemia and protects against IRI in a feline model of mesenteric ischemia. The general consensus is that iNO increases the circulating levels of a stable NO-donor and includes S-nitrosothiol (SNOs) and nitrite. We recently conducted a double-blinded randomized controlled trial whereby, 80 ppm of iNO was administered to patients undergoing orthotopic liver transplantation (16). Many advantages were reported in the iNO group, including reduced platelet transfusion, an improvement in the rate at which liver function was restored post-transplantation, and a decrease in the length of hospital stay. Most interesting was the finding of an approximated 75% reduction of hepatocellular apoptosis in patients treated with iNO. Moreover, of the possible biochemical intermediates formed from iNO in the plasma (nitrate, nitrite, S-nitrosothiols, C- or N-nitroso compounds), the most likely candidate transducer of iNO on liver IRI was concluded to be nitrite.

Webb, A., et al showed that nitric oxide derived from the reduction of nitrite protected against myocardial ischemia/reperfusion damage. Duranski et al. showed cytoprotective effects of nitrite in heart and liver. Jung et al showed protection of the brain in ischemia-reperfusion injury in the brain. These findings suggest an opportunity for nitrite therapy for human diseases associated with ischemia-reperfusion. The goal of this application is to test nitrite therapy in human islet cell autotransplantation and to test the hypothesis (related to the bedside component of this funding mechanism) that nitrite will protect the transplanted islet cells from ischemic injury during procurement and reperfusion injury following islet cell infusion into the liver sinusoids. Furthermore, if the data support the central hypothesis, nitrite infusion may lead to marked reduction in the amount of long term insulin requirement and perhaps, a higher rate of cure.

3.0 ELIGIBILITY CRITERIA

All patients will be enrolled into the study at the University of Alabama at Birmingham Medical Center (UAB). Approximately 18 islet cell autotransplantations are conducted at UAB annually by one surgeon, thereby eliminating the need to include surgical technique as a possible confounding variable.

Based on our prior experience conducting similar studies, we anticipate that approximately 80% of patients undergoing islet cell autotransplantation meet enrollment criteria and agree to the written informed consent. Accordingly, we conservatively estimate that it will take approximately two years to complete enrollment for the study, followed by a third year for data analysis and study closeout.

3.1 Inclusion criteria

The study sample will include 30 adult (≥ 19 years of age) patients of either gender with acquired insulin dependent diabetes mellitus who provide informed written consent and:

- Patients admitted to UAB for islet cell autotransplantation
- >18 years old

3.2 Exclusion Criteria

Any patient with liver disease or unsuitable for surgery (as determined by surgeon).

4.0 RECRUITMENT PROCEDURES

4.1 Recruitment

Thirty (30) patients will be enrolled – 10 patients in each arm of the study. Patients will be screened and recruited by the patient coordinator in [name] clinic. The coordinator will confirm eligibility and absence of any exclusionary criteria. Details of the study (including risks) will be explained to prospective participants and an informed, signed consent form will be obtained from participants.

4.2 Randomization Procedure

This is a single institution, blinded, placebo-controlled clinical trial. Patients will be randomized to one of three (3) arms of the study by the research pharmacist:

- Control group (saline infusion will be administered during the pre-isolation and post-isolation phases)

- Pre-isolation infusion (nitrite infusion will be administered during the pre-isolation phase and saline will be administered during the post-isolation phase)
- Post-isolation (saline will be administered during the pre-isolation phase and nitrite infusion will be administered during the reperfusion phase)

Continuous infusion of 32 mg sodium nitrite in 100 mL normal saline at a rate of 10 mL per min over for the duration of the surgery, which are calculated to achieve steady-state plasma concentrations of approximately 10 μ M, concentrations shown to have therapeutic efficacy in animal models of IRI.

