5.0 EXPERIMENTAL PROTOCOL

Protocol Design:

This is a single institution, randomized, placebo-controlled clinical study. There will be 3 cohorts: control group, pre-isolation nitrite infusion, and a post-isolation (reinfusion) cohort.

After induction of general anesthesia with propofol (1-1.5 mg/Kg), tracheal intubation, the establishment of central venous access, invasive monitors and maintenance anesthesia with sevoflurane (1-1.5 minimum alveolar concentration) in 50:50 oxygen: air, infusions will be administered based on the randomization assignment.

I. Control Group A placebo (saline infusion) will be administered during the pre-isolation phase and during the reinfusion phase.

II. Pre-Isolation Infusion Group

[figure not shown]

Figure 1: Pre-isolation group schematic: Sodium nitrite will be initiated (pre-isolation infusion group) during the pre-isolation phase. Saline will be administered during the reperfusion period.

III. Post-Isolation (Reinfusion) Group

[figure not shown]

Figure 2: Reinfusion group schematic: Saline will be administered during the pre-isolation period. Sodium nitrite infusion will be initiated just prior to the reinfusion.

For all 3 groups:

Intraoperative arterial and venous blood samples (BS) will be drawn immediately prior to initiation of the infusion (BS1), 5 min prior to infusion of Islet Cells (BS2), 20 min after infusion of Islet Cells (BS3), and 40 min after infusion of Islet Cells (BS4).

Postoperative blood samples will be obtained 24, 48, 72 and 96 hours after the completion of surgery.

Results of routine lab work performed at the routine 3 month follow-up visit will be collected.

Procedure for Sample collection (email from [name] 6/28/16) – to be performed by lab tech in BMR

- 1) *Transferring blood to Eppendorf tubes,*
- 2) *Centrifuging (using a table top min-fuge which we can provide),*
- 3) *Transferring plasma to 4 other vials (1 containing a pre-made solution, which we can provide) and flash freezing all vials in liquid N₂*
- 4) *Taking some of the red cell pellet and adding to vials (containing pre-made solution that we can provide) and flash freezing all vials in liquid N₂*
- 5) *All samples need to be stored at -80C.*

Primary Endpoints:

- Markers of pancreatic function:
 - Blood glucose levels
 - HbA1c levels pre-operatively and at the 3 month post-operative visit
 - Exogenous insulin use
 - Measured from blood samples 24, 48, 72, 96 hours post op & at 3 months post op

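### The only nitrite dosing sentence (4.2) does not define a workable regimen: as a total dose it runs out in 10 minutes, and as a concentration it gives 192 mg per hour with no stated limit

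*Combined protocol and SAP*

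**What the plan says.** Section 4.2 gives the amount, volume, rate and duration of nitrite in one sentence, a continuous infusion specified as "32 mg sodium nitrite in 100 mL normal saline at a rate of 10 mL per min over for the duration of the surgery". It adds that the infusion is "calculated to achieve steady-state plasma concentrations of approximately 10" μM. No other visible section gives a nitrite amount or rate.

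The same section limits nitrite to one phase in each active arm:

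- Pre-isolation arm: "nitrite infusion will be administered during the pre-isolation phase and saline will be administered during the post-isolation phase".
- Post-isolation arm: "saline will be administered during the pre-isolation phase and nitrite infusion will be administered during the reperfusion phase".

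Section 5.0 repeats this allocation. It says that "infusions will be administered based on the randomization assignment", and the Figure 2 caption for the post-isolation arm says "Sodium nitrite infusion will be initiated just prior to the reinfusion".

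Section 5.0 gives no operating time, but its list of intraoperative samples ends with one taken "40 min after infusion of Islet Cells (BS4").

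Section 8.0 says that Phase I studies in more than 80 volunteers used this trial's planned doses without observed toxicity. It does not state those doses.

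**The concern.** Amount, volume, rate and time in an infusion instruction have to agree, because any three of them fix the fourth. Here the first three imply a time much shorter than the one stated. The pharmacist preparing the infusion and the anesthesiologist running it must decide for themselves whether to stop after one bag or keep replacing bags.

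Two things are at stake. The first is safety. The study drug is given intravenously to surgical patients, and 8.0 names methemoglobin formation and platelet inhibition as the main clinical concerns. The second is what the trial estimates. With 10 patients per arm, a nitrite arm in which some patients receive 32 mg and others several times as much has no single treatment to compare with saline. If everyone received one 10-minute bag, a null result would say little about the continuous exposure that the protocol seems to intend.

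**Working it through.** **Inputs.** From 4.2: 32 mg, 100 mL, 10 mL/min, and a duration equal to the surgery. From 5.0: the last intraoperative sample (BS4) is 40 min after islet infusion, and BS2 is 5 min before it. The length of surgery and of each phase is not given.

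**Reading A: 32 mg is the total dose.**

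- Run time = volume / rate = 100 / 10 = 10 min.
- Delivery rate = 32 / 10 = 3.2 mg/min.
- Because BS4 is intraoperative, surgery continues at least 40 min after islet infusion, and BS2 to BS4 spans at least 40 + 5 = 45 min. A 10-minute infusion cannot cover the surgery.

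**Reading B: 32 mg per 100 mL is a concentration, with bags replaced.**

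- Concentration = 32 / 100 = 0.32 mg/mL.
- Delivery rate = 0.32 × 10 = 3.2 mg/min, the same as in reading A.
- Per hour: 10 × 60 = 600 mL (six bags) and 600 × 0.32 = 192 mg.
- The total is 3.2 mg/min multiplied by a nitrite time that the visible text does not give.

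| Nitrite time (assumed, for illustration) | Reading A | Reading B | Volume, reading B |
|---|---|---|---|
| 1 h | 32 mg | 192 mg | 600 mL |
| 2 h | 32 mg | 384 mg | 1,200 mL |
| 4 h | 32 mg | 768 mg | 2,400 mL |

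At one hour the ratio is 192 / 32 = 6. No total per arm can be computed, because the phase lengths are unknown.

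**The 10 μM target.** Both readings deliver 3.2 mg/min and differ only in how long. The target therefore does not show which reading is meant. Nor can it be checked, since no clearance or volume of distribution is given.

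**The duration clause against the arms.** Taken literally, nitrite throughout surgery would reach both active arms in both phases. Sections 4.2 and 5.0 give the pre-isolation arm saline during reperfusion, and the post-isolation arm saline until shortly before reinfusion. The clause and the allocation cannot both be followed as written.

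**The case against.** The strongest defence is that reading B is the natural one. A continuous infusion aimed at a steady-state level is defined by its concentration and rate, and its total varies with operating time. On that reading the sentence is incomplete, not contradictory. This stands: a reader might infer that the instruction is flatly impossible, and the documents do not support that. Reading B is still not stated, however, and it leaves 600 mL and 192 mg per hour with no upper limit.

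A reader might also infer that the 10 μM target must fail under one of the readings. That does not follow, because the delivery rate is the same in both. It would matter only if the rate itself were misprinted, and nothing in the documents shows that. Whether 10 minutes is long enough to reach steady state cannot be judged without kinetic data.

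The doubled preposition before the duration may mark a lost time, through drafting or text extraction. This is possible, so the statement that no total is given applies to the visible text only. A recovered time would not rescue reading A: only 10 minutes fits the volume and rate, and that is not the length of the surgery. Figures 1 and 2 are not shown and may mark when infusions stop, so no claim is made that stop points are missing.

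On the phase conflict, a reader might infer that the active arms are undefined. They are not: the allocation is stated in both 4.2 and 5.0, and the intended contrast is clear. The duration clause is what needs to change.

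Section 8.0 limits harm through methemoglobin measurement with a stop at 5%, a stop for bleeding or abnormal coagulation, and DSMB oversight. These safeguards act after exposure. They neither define the dose nor detect under-dosing. The Phase I sources are not available, so no mismatch with the planned doses can be shown; the statement just has no single regimen to refer to.

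**Conclusion.** The concern holds as a failure to define the regimen. One reading cannot meet the stated duration, and the other, better supported, has no visible limit. The 10-minute run time and the hourly figures of 192 mg and 600 mL are exact arithmetic on the protocol's own numbers. The 6-fold difference assumes one hour of nitrite. The 40-minute bound rests on BS4 being listed as intraoperative. Confidence is high that the sentence is ambiguous and that its duration clause conflicts with the one-phase arms. The documents do not show which figure, if any, is wrong. Because this is the only instruction for giving the study drug, the correction is essential, not editorial.

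**What to change.** Amend the dosing sentence in 4.2 to:

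1. State whether 32 mg is the total dose or 32 mg per 100 mL is a concentration. If it is a concentration, say that bags are replaced.
2. Make amount, volume, rate and time agree. Which figure to change is for the sponsor to decide.
3. Replace the whole-surgery duration with the assigned phase for each nitrite arm: the pre-isolation phase only, or from shortly before reinfusion through the reperfusion phase, with saline otherwise.
4. State a maximum dose or a maximum duration.

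Then confirm that the 10 μM target in 4.2 and the Phase I dose statement in 8.0 both refer to the amended regimen.

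The cost is an amendment to one sentence and a sponsor check of two existing statements. No extra patients, visits or samples are needed.

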8.0 SAFETY MONITORING

The intraoperative anesthetic and postoperative intensive care management of these patients will be the responsibility of the anesthesiologist or critical care physician, respectively.

Possible Adverse Events: Primary clinical concerns include the formation of methemoglobin and inhibition of platelet function. Phase I studies of sodium nitrite infusion have been completed in more than 80 normal human volunteers at the doses planned for this trial with no observed toxicity (e.g., no clinically significant increases in methemoglobin or hypotension). Nevertheless, plasma methemoglobin will be measured throughout the intraoperative and immediate postoperative periods. The study drug will be discontinued should methemoglobin levels increase to 5% or greater. Parameters related to coagulation and bleeding will be monitored per standard of care. Adverse coagulation or excessive bleeding will lead to immediate cessation of study drug. Based on our prior experience with inhaled NO (**Lang REF**), we do not anticipate increased bleeding relative to placebo and anticipate that metHb levels will remain $< 5\%$ for the duration of nitrite administration

Assessment of Level of Risk: Very low (numerous studies have established safety of nitrite infusion).

Oversight of this investigation will be provided by the PI, surgeon, and co-investigators. They will be responsible for all aspects of the conduct of the trial.

Safety oversight will be provided by the Data and Safety Monitoring Board (DSMB).

9.0 Adverse Events Reporting: This study poses minimal risk.

10.0 References:

4. XIAP overexpression in islet beta-cells enhances engraftment and minimizes hypoxia-reperfusion injury. Emamaullee J, Liston P, Korneluk RG, Shapiro AM, ...

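### The nitrite dose sentence in section 4.2 is internally inconsistent: the stated bag is empty in 10 minutes, yet the infusion is to be continuous throughout surgery, and no total dose is given

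*Combined protocol and SAP*

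**What the plan says.** Section 4.2 (Randomization Procedure) holds the only readable dosing instruction for the study drug. It describes a continuous infusion, specified as "32 mg sodium nitrite in 100 mL normal saline at a rate of 10 mL per min over for the duration of the surgery", and says the infusion is "calculated to achieve steady-state plasma concentrations of approximately 10" µM, a level it links to efficacy in animal models.

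Each active arm receives nitrite in one phase only. In the pre-isolation arm, "nitrite infusion will be administered during the pre-isolation phase and saline will be administered during the post-isolation phase". In the post-isolation arm saline comes first and then "nitrite infusion will be administered during the reperfusion phase". The figure legends in section 5.0 (Experimental Protocol) give the starts: "Sodium nitrite will be initiated (pre-isolation infusion group) during the pre-isolation phase" and "Sodium nitrite infusion will be initiated just prior to the reinfusion". The figures themselves are not shown in the text available for review.

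Section 5.0 also lists intraoperative blood samples before the study infusion (BS1), 5 minutes before islet infusion (BS2), and "20 min after infusion of Islet Cells (BS3), and 40 min after infusion of Islet Cells (BS4").

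Section 8.0 (Safety Monitoring) names methemoglobin formation and impaired platelet function as the main clinical concerns. Its reassurance is that more than 80 volunteers have been studied "at the doses planned for this trial with no observed toxicity". It adds methemoglobin measurement, a stopping rule at 5%, cessation for bleeding or coagulation problems, and DSMB oversight. No readable section gives a total or maximum nitrite dose, a duration in minutes, a statement on bag replacement, or the pharmacokinetic inputs behind the 10 µM figure.

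**The concern.** The dose sentence contains four elements: an amount, a volume, a rate and a duration. The first three fix the running time, and it does not match the fourth. One pharmacist could reasonably prepare a single bag and stop when it is empty. Another could reasonably keep hanging bags until the phase or the operation ends. Both could claim to be following section 4.2, and their patients would receive doses that differ several-fold.

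Two things are at stake. The first is safety: the drug is intravenous, its main toxicity is named in the protocol, and the reassurance in section 8.0 depends on a planned dose whose total is not stated. The second is interpretation: with 10 patients per arm, variation in delivered dose would make it hard to attribute any result to a particular regimen. The 10 µM level, which is the plan's stated link to the animal evidence, would not belong to any defined regimen either.

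**Working it through.** **Inputs from the plan**

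- Section 4.2: 32 mg sodium nitrite, 100 mL, 10 mL/min, steady-state target about 10 µM.
- Section 5.0: BS2 at 5 minutes before islet infusion and BS4 at 40 minutes after, both intraoperative.
- Assumption: molar mass of sodium nitrite 69 g/mol (not in the plan).

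**1. The plan's own figure.** Steady-state level = infusion rate / clearance. The plan gives no clearance, half-life, volume of distribution or body weight, so the 10 µM figure cannot be reproduced.

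**2. Running time and dose rate.**

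- Running time: 100 mL / 10 mL/min = 10 min.
- Dose rate: (32 mg / 100 mL) × 10 mL/min = 3.2 mg/min.
- Dose in one bag: 3.2 mg/min × 10 min = 32 mg.

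**3. Minimum length of the operation.** From BS2 to BS4 is at least 5 + 40 = 45 min, not counting the time from BS1 to BS2. One bag at the stated rate therefore cannot last through surgery.

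**4. Possible readings of the sentence.**

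| Reading | Consequence | Wording it breaks |
|---|---|---|
| One bag at 10 mL/min | 32 mg over 10 min | the duration; steady-state becomes doubtful |
| 0.32 mg/mL at 10 mL/min, bags replaced | 600 mL and 192 mg per hour (6 bags) | none directly, but replacement and a cap are unstated |
| One bag spread over the operation | for example 100/60 = 1.67 mL/min if it lasted 1 h (assumed) | the rate |

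The hourly figures for the second reading are 10 mL/min × 60 min = 600 mL and 3.2 mg/min × 60 min = 192 mg. One hour on that reading delivers 192/32 = 6 times one bag.

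**5. Illustration on the plan's own clock.** Suppose nitrite ran at the stated rate from islet infusion to BS3. That is 20 × 3.2 = 64 mg in 200 mL. To BS4 it is 40 × 3.2 = 128 mg in 400 mL, or four bags. These are sampling times, and the plan does not say that nitrite runs until then. The figures show only how quickly the readings diverge.

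**6. What 10 µM would require under each reading (illustration).**

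- Dose rate: 3.2 mg/min / 69 g/mol = 46.4 µmol/min.
- Maintained infusion: clearance = 46.4 / 10 = 4.64 L/min.
- One bag in 10 min: 32 mg = 463.8 µmol. With one well-mixed compartment, a level of 10 µM at the end of the bag needs a volume of at most 463.8 / 10 = 46.4 L. Any elimination lowers that limit.
- One bag over an assumed 1 h: 463.8 / 60 = 7.73 µmol/min, so clearance = 0.77 L/min.

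All of these ignore baseline nitrite. The same target implies different pharmacokinetics under each reading, and the plan supplies no value that would tell the reader which one was used.

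**The case against.** The best defence is that 32 mg in 100 mL is a concentration. Nothing in section 4.2 calls it a total dose or a single bag. On that reading the order is workable: 0.32 mg/mL at 10 mL/min for a period. The words continuous and steady-state both lean that way. This stands, and so a reader who infers that the order is impossible to carry out goes further than the text allows. It does not rescue the sentence, because bag replacement is never mentioned and an infusion at 192 mg per hour is left without a total or a cap.

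A reader might also infer that the plan gives no stopping point for nitrite. That is too strong. In the pre-isolation arm the change of phase ends nitrite. In the post-isolation arm the end of surgery is a natural stop, and the two missing figures may mark more. Nor does the reference to the length of surgery have to conflict with the single-phase arms, since it can describe the whole blinded sequence of nitrite and saline. The stop-time point is therefore secondary. The figures could not, however, make 100 mL at 10 mL/min last beyond 10 minutes.

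The odd wording before the duration (over followed by for) suggests that a time was dropped, in drafting or in the reading of the PDF. What was lost is unknown. If it was 10 minutes, it would still clash with an infusion lasting the operation.

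Finally, section 8.0 has real safeguards: methemoglobin measurement, the 5% rule, cessation for bleeding, and a DSMB. They limit harm once exposure has begun. They do not tell the pharmacist what to prepare.

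**Conclusion.** The concern holds as an internal inconsistency with an undefined total dose. The 10-minute running time and the 3.2 mg/min rate are exact and need no assumption. What follows depends on the reading: 32 mg in total for one bag, or 192 mg and 600 mL for every hour of a maintained infusion. The text leans toward the second without saying so. The rate is defined, but section 8.0's reliance on the planned doses cannot be tied to one total dose.

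A reader might conclude from the back-calculated clearance or volume that 10 µM is wrong. The documents do not support that: they give no value to compare, so the figure is unsupported and not shown to be false. A reader might also take 64 or 128 mg as the dose that patients will receive. Those amounts depend on an assumed running time and are illustrations only. This review does not say which regimen was intended. Because the sentence governs the dose of an intravenous drug with a named toxicity, it should be corrected before any patient is dosed.

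**What to change.** Rewrite the dose sentence in section 4.2, and align section 5.0 with it. For each active arm, state:

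- one infusion rate;
- the infusion duration, with a start and a stop given as an event or a time;
- the resulting total nitrite dose, or a maximum if the duration varies between patients;
- whether bags are replaced.

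Restate the 10 µM target as the level predicted for that regimen, preferably with the clearance and half-life used. Drop the term steady-state if the infusion lasts only 10 minutes. In section 8.0, confirm that the volunteer experience relied on covers the same rate and total dose.

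The cost is a corrected sentence and a short pharmacokinetic calculation. The drawback is that the stated exposure, once made explicit, may look less favourable than the present wording suggests, and pharmacy or DSMB review may be needed before dosing.
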